**Secondary Outcomes:** Secondary outcomes will be used to provide preliminary information about effectiveness, taking into consideration the limited sample size for the pilot project. *HIV-related outcomes* (the primary outcomes for the eventual full-scale trial) will be defined as (a) *viral suppression at 6 months*, and (b) HIV appointment adherence between baseline and 12 months of follow up. Viral load will be captured from clinical records, or ordered by the study if no viral load is collected in the appropriate window. HIV appointment attendance will be evaluated by measuring the proportion of scheduled visits in the 12-month follow-up period that are attended vs. no-shows (the “kept visit proportion”), with no show defined as no appointment kept in the 30 days following a scheduled appointment. HIV appointment data will be abstracted from clinic records at the end of the study period.

*Mental health outcomes* (the secondary outcomes for the eventual full-scale trial) will be defined as DASS-21 total score indicating any CMD symptoms as well as mean subgroup scores for depression, anxiety, and stress at 6 weeks after enrollment (FB: treatment exit) across all study arms. We will consider both the simple severity level at follow-up as well as the absolute reduction in symptoms from baseline.

*Methadone maintenance engagement* (another secondary outcome for the full trial) will be defined as the proportion of days with methadone maintenance therapy adherence measured from study baseline through 12 months of follow up.

**Additional (tertiary) outcomes:** Tertiary *HIV-related outcomes* will be defined as (a) viral suppression at 12 months and (b) consistent ART use over 12 months as confirmed by clinical records. Tertiary *mental health outcomes* will be defined as DASS-21 total score indicating any CMD symptoms as well as subgroup scores for depression, anxiety, and stress at 3 months, 6 months, and 12 months across all study arms. We will consider both the simple severity level at follow-up as well as the absolute reduction in symptoms from baseline.

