### 3.2 Population

#### Inclusion criteria

Eligible individuals will be adult patients (18 years and older) being treated at the MMT clinic  
IRB# 20-1689

Protocol v3.0 2023-10-01

whose medical record indicates infection with HIV will be screened with the DASS-21, which has been translated, standardized and validated in the Vietnamese population. The DASS-21 assesses symptoms of depression, anxiety and stress among adults. The respondent is asked to think about their experiences in the past seven days and to rate each of the 21 items along a 4-point scale from 0 ("Did not apply to me at all–Never") to 3 ("Applied to me very much, or most of the time–Almost always"). There are three subscales, each with 7 items (DASS-21-Depression, DASS-21-Anxiety, and DASS-21-Stress) allowing calculation of three subgroup scores (0-21) and a total score (0-63). We then use these totals to identify the likelihood of a depressive disorder, an anxiety disorder, a stress-related disorder, or any of the three. Consistent with our prior work and with prior validation studies in the Vietnamese population, we will consider as eligible all patients with a depression subscale score  $\geq 7$ , an anxiety subscale score  $\geq 6$ , and/or a stress subscale score  $\geq 10$ . These cut-offs indicate at least a moderate severity of symptomatology. Further, to ensure that we are identifying clinically meaningful CMDs rather than transient mood fluctuations, we will require that elevated depressive symptoms be present for  $\geq 2$  weeks and elevated anxiety or post-traumatic stress-related symptoms be present for  $\geq 1$  month. We will consider a positive screen for any of the three categories as indicating a CMD.

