### 3.5 Data Sources

Sources of data for this study include the participant baseline and follow-up assessments, provider semi-structured interviews, audio recordings of counseling sessions that will be rated for fidelity, and medical record data (to collect HIV appointment attendance and viral loads). We will capture viral load from medical records when possible; if no viral load is scheduled at the requisite time point for the study, then the study will order and pay for a viral load test. Blood samples for study viral loads will be drawn by the same clinic staff and in the same manner as clinic-ordered viral loads

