## 4.0 ANALYSIS

**Statistical Analysis.** Feasibility, acceptability, and fidelity will be evaluated using descriptive statistics. We will compare mean fidelity scores between the professional FB and lay FB counselors using an intent-to-treat approach, using a robust variance estimator to account for multiple observations per counselor. Means and proportions for HIV-related and mental health outcomes will be compared between arms using an intent-to-treat analysis approach.

We will evaluate effectiveness measures comparing professional counselors to enhanced usual care and lay counselors to enhanced usual care. Considering the purpose of this small pilot trial, our focus will be on estimating effect size and precision rather than statistical significance and hypothesis testing. To take advantage of the repeated-measures nature of the outcome data, we will also fit generalized estimating equation (GEE) regression models, using a link appropriate for each outcome (i.e. identity link for continuous variables and log link for binary variables), to simultaneously examine differences in outcomes at 6 weeks, 3 months, 6 months and 12 months between the arms. Given the relatively small sample size, it is possible that important predictors of outcome (such as baseline mental health symptom severity or time in HIV care) could end up being unbalanced between arms; if this is the case we will conduct secondary regression analyses adjusting for the unbalanced potential confounder.

In **secondary analyses**, we will examine whether HIV-related, MMT, and mental health outcomes vary by proportion of FB sessions attended and by number of elevated symptom domains at baseline (depression, anxiety, and/or post-traumatic stress).

In **moderation analyses**, we will explore whether severity of illness (duration; symptom severity; family history) modifies any preliminary evidence of efficacy in primary outcomes, while recognizing that a pilot trial is not designed to be powered to statistically test modification hypotheses.

**Missing data.** Every effort will be made to minimize missing data, including collecting detailed locator information for the participant as well as for up to three individuals who could help reach the participant should they drop out of contact. However, some missing

IRB# 20-1689

Protocol v3.0 2023-10-01

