## 7.0 WORKPLAN

**Timeline.** The Friendship Bench adaptation will be completed in year 1 quarter 3. The pre-pilot RCT to test materials and study procedures will begin in year 1 quarter 4 and will last 3 months. The 3-arm pilot study will begin in year 2 quarter 1, with recruitment completed

within a 3-month period. Given that MMT/ART patients attend clinic daily for directly observed MMT, we anticipate little difficulty fully enrolling within a 3-month period. However, we have enough leeway in our timeline to extend enrollment if needed to achieve our target sample size. Treatment will be completed by the middle of year 2, while research follow-up through 12 months will be completed by the middle of year 3. Feasibility and fidelity assessment will be ongoing throughout the trial, while patient acceptability assessments will be folded into the research outcome interviews. The remainder of year 3 will focus on data analysis and dissemination, manuscript preparation, and planning for the follow-up R01 RCT. We expect to generate a minimum of 3 manuscripts from this pilot study.

Activity	Year 1				Year 2				Year 3			
	Q1	Q2	Q3	Q4	Q1	Q2	Q3	Q4	Q1	Q2	Q3	Q4
IRB Regulatory												
Aim 1 - Adaptation to improve CMDs and engagement in PWID with HIV												
Adapt Friendship Bench; feedback; finalize												
Aim 2 Approach - Pilot study of Friendship Bench in PWID with HIV												
Prepilot followed by 3-arm pilot study recruitment: 3 months												
Pilot study treatment sessions: ~3 months w/ follow-up through 12 months												
Aim 2 Outcomes- Assessment of feasibility, acceptability, fidelity, and preliminary indicators of impact												
Feasibility, acceptability, fidelity measurement												
Preliminary indicators of impact: Research interview at 3, 6, and 12 months												
Dissemination												
Data analysis and dissemination, manuscript preparation, RCT planning												

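### The plan collects no pre-baseline record of kept HIV visits or methadone days and names no prior-attendance covariate, which gives up precision on both engagement outcomes

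*Combined protocol and SAP*

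**What the plan says.** **Outcomes.** The paragraph on secondary outcomes in Section 3.0 sets two engagement measures. The HIV measure is "HIV appointment adherence between baseline and 12 months of follow up", scored as the "proportion of scheduled visits in the 12-month follow-up period that are attended vs. no-shows". The methadone measure is the "proportion of days with methadone maintenance therapy adherence measured from study baseline through 12 months of follow up". Both clocks start at baseline.

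**Sources.** Section 3.0 says that "HIV appointment data will be abstracted from clinic records at the end of the study period". Section 3.5 lists "medical record data (to collect HIV appointment attendance and viral loads". Methadone days are not in that list, and no other section gives a source for them. The baseline assessment in Section 3.0 covers sociodemographics, self-reported health, the MINI, a urine drug screen, the Time Line Follow Back and psychosocial factors. It names neither past HIV visits nor past methadone dosing.

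**Adjustment.** Section 3.0 does not stratify the randomization and offers adjusted analyses if a problematic imbalance appears. Section 4.0 takes this up, noting that "important predictors of outcome (such as baseline mental health symptom severity or time in HIV care) could end up being unbalanced between arms", and plans secondary adjusted regressions in that case. Only the DASS-21 gets an analysis of change from baseline.

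**History at entry.** Section 3.2 reads: "Eligible individuals will be adult patients (18 years and older) being treated at the MMT clinic". The medical record must also show HIV infection. Section 7.0 states that "MMT/ART patients attend clinic daily for directly observed MMT".

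**The concern.** A patient's attendance over the past months is a natural candidate to predict attendance over the next twelve, and most participants should have some history at the clinic when they enter. The plan neither collects that history nor names it as a covariate. Its only safeguard is to adjust for predictors that turn out unbalanced, and imbalance cannot be seen in a variable that nobody abstracts.

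The stake is precision. Section 4.0 puts the weight on the size of effects and how precisely they are known, not on tests. Kept HIV visits are a planned primary outcome of the later full trial, and methadone engagement a planned secondary one. Without prior attendance, the pilot also cannot estimate the correlation between prior and follow-up attendance, which would be needed to size an adjusted analysis in that trial.

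**Working it through.** **1. The plan's own precision figure.** Section 3.4 gives an example for elevated symptoms: RR 0.63 with 95% CI 0.38 to 1.00, at 25 per arm and 80% retention (20 per arm). It gives no event rates. Trying event counts, 10/20 against 16/20 comes close:

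- SE of log RR = sqrt(1/10 − 1/20 + 1/16 − 1/20) = sqrt(0.0625) = 0.25
- RR = 0.50/0.80 = 0.625; CI = 0.625 × exp(±1.96 × 0.25) = 0.38 to 1.02

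The example therefore reproduces approximately. The plan gives no such figure for kept visits or methadone days, so the rest is in SD units.

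**2. Inputs.** Arm size n is 25, or 20 at 80% retention (Section 3.4). The correlation r between pre-baseline and follow-up attendance is not in the documents; 0.3, 0.5 and 0.7 are assumptions.

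**3. Formulas.** For a difference in means between two arms:

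- Unadjusted 95% half-width = 1.96 × sqrt(2/n) SD
- Adjusted for prior attendance = 1.96 × sqrt(2/n) × sqrt(1 − r²) SD
- Sample size without adjustment that gives the same precision = n / (1 − r²)

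**4. Results.** Unadjusted half-width: 1.96 × sqrt(2/25) = 0.55 SD, or 1.96 × sqrt(2/20) = 0.62 SD.

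| Assumed r | sqrt(1 − r²) | CI narrower by | Half-width, n = 25 | Half-width, n = 20 | 1/(1 − r²) |
|---|---|---|---|---|---|
| 0.3 | 0.954 | 5% | 0.53 | 0.59 | 1.10 |
| 0.5 | 0.866 | 13% | 0.48 | 0.54 | 1.33 |
| 0.7 | 0.714 | 29% | 0.40 | 0.44 | 1.96 |

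The last column means that adjustment is worth 10%, 33% or 96% more patients. A small-sample allowance for estimating one extra coefficient, the factor sqrt(1 + 1/(2n − 4)), moves the n = 25 half-widths only to 0.535, 0.485 and 0.400.

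**5. Chance imbalance.** The difference between two arms in mean prior attendance has SD sqrt(2/25) = 0.283. A gap above 0.25 SD has probability 0.38 at 25 per arm and 0.43 at 20; a gap above 0.5 SD has probability 0.08 and 0.11.

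**6. Is that imbalance an additional harm?** Take r = 0.6 and n = 25. The part of the 95% sampling error that comes from prior attendance is 0.6 × 0.554 = 0.33 SD. The rest is sqrt(1 − 0.36) × 0.554 = 0.44 SD. Since 0.33² + 0.44² ≈ 0.55², the 0.33 SD already lies inside the unadjusted interval. Steps 4 and 5 describe one loss from two sides.

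**The case against.** The strongest reply is that nothing here is wrong. An outcome after randomization should be measured from baseline forward, and the unadjusted intent-to-treat comparison is unbiased. These are secondary outcomes of a 75-patient pilot whose primary outcomes (feasibility, acceptability, fidelity) are untouched, and there is no power target to miss. All of that stands, and it limits the point to efficiency.

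The size is also uncertain. The formula assumes a linear relation between two continuous measures. Kept visits are a bounded proportion with a 30-day grace period, and the number of scheduled visits is not given. If a look-back window holds few visits, r may be near 0.3 and the gain near 5%. This stands too.

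A reader might infer several stronger things that the documents do not support:

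- **That prior attendance is out of reach.** It is only unplanned. HIV appointments are abstracted retrospectively, so the same exercise can look further back.
- **That methadone days come from the same clinic records.** No source is named. Daily observed dosing makes dosing records likely, but that is inference.
- **That every participant has a usable HIV-care history.** Section 3.2 requires treatment at the MMT clinic and HIV infection on record, with no minimum time in care.
- **That the adjustment rule is limited to symptom severity and time in HIV care.** Those are examples. Prior attendance would be allowed if it were collected. The baseline assessment is also listed by domain, so a question on past attendance is not excluded, but none is named.

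The reply does not remove the gap itself: no pre-baseline window is defined, no covariate is pre-specified, and the imbalance rule has no such data to act on.

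**Conclusion.** The point holds as a cheap improvement. For kept HIV visits and methadone days the plan defines no pre-baseline window and pre-specifies no prior-attendance covariate. The cost is precision: adjustment would narrow the interval by about 5%, 13% or 29% at assumed r of 0.3, 0.5 or 0.7, with the low end more likely where histories are short or visits few. These figures rest on the assumed correlations and on a linear model; the documents supply neither.

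A reader might take the possible shift from chance imbalance (0.33 SD at r = 0.6) as bias, or as harm on top of the wide interval. It is neither: randomization protects the comparison on average, and the shift is part of the sampling error that the unadjusted interval already covers.

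**What to change.** 1. **Sections 3.0 and 3.5:** extend the end-of-study HIV appointment abstraction to a fixed window before randomization, for example 6 months, or since entry to care if shorter, with an indicator for a shortened history. Score it by the same kept-visit rule as the outcome.
2. **Sections 3.0 and 3.5:** name the data source for methadone days. If it is clinic dosing records, abstract the same window.
3. **Section 4.0:** for these two outcomes, pre-specify the matching pre-randomization proportion as a covariate regardless of observed imbalance, and keep the unadjusted comparison alongside.

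Records from before randomization cannot be affected by the assigned arm, so collecting them retrospectively is valid.

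The cost for HIV visits is a longer look-back in an abstraction already planned, or a return to the records if it has been done. For methadone days the cost depends on the source, since no abstraction is currently described. Recent entrants will have incomplete histories, and the team must confirm that consent and ethics approval cover the look-back.

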### 3.1 Study Sites

The proposed study will be conducted at 4 public MMT clinics in the Hanoi, Vietnam area where we have successfully enrolled patients in prior studies. Each of the 4 health centers provides methadone maintenance treatment (MMT) to individuals with opioid use disorder as well as integrated HIV/ART care to those additionally living with HIV. Male users make up the vast majority of individuals with opioid use disorder here. In Vietnam, PLWH and OUD typically get integrated treatment with ART and methadone at district health centers. Thus, the co-location of HIV and MMT services makes these health centers ideal locations to serve PLWH with OUD. CMD screening and assessment are rare to nonexistent at HIV/MMT clinics in Hanoi, as in most clinical settings in Vietnam.

UNC Project in Vietnam will serve as the administrative home for the study and has longstanding relationships with all 4 proposed study sites, the Ministry of Health, and CDC Hanoi. Approximately 80 individuals living with HIV and with OUD present monthly at each site, providing adequate numbers for aim 2. UNC Project has previously successfully recruited and enrolled PLWH on MMT

### 3.2 Population

#### Inclusion criteria

Eligible individuals will be adult patients (18 years and older) being treated at the MMT clinic  
IRB# 20-1689

Protocol v3.0 2023-10-01

whose medical record indicates infection with HIV will be screened with the DASS-21, which has been translated, standardized and validated in the Vietnamese population. The DASS-21 assesses symptoms of depression, anxiety and stress among adults. The respondent is asked to think about their experiences in the past seven days and to rate each of the 21 items along a 4-point scale from 0 ("Did not apply to me at all–Never") to 3 ("Applied to me very much, or most of the time–Almost always"). There are three subscales, each with 7 items (DASS-21-Depression, DASS-21-Anxiety, and DASS-21-Stress) allowing calculation of three subgroup scores (0-21) and a total score (0-63). We then use these totals to identify the likelihood of a depressive disorder, an anxiety disorder, a stress-related disorder, or any of the three. Consistent with our prior work and with prior validation studies in the Vietnamese population, we will consider as eligible all patients with a depression subscale score  $\geq 7$ , an anxiety subscale score  $\geq 6$ , and/or a stress subscale score  $\geq 10$ . These cut-offs indicate at least a moderate severity of symptomatology. Further, to ensure that we are identifying clinically meaningful CMDs rather than transient mood fluctuations, we will require that elevated depressive symptoms be present for  $\geq 2$  weeks and elevated anxiety or post-traumatic stress-related symptoms be present for  $\geq 1$  month. We will consider a positive screen for any of the three categories as indicating a CMD.

#### Exclusion criteria

Those with evidence of psychosis or bipolar disorder per the MINI will be excluded.

### **3.3 Duration**

Aim 1 (protocol adaptation) will be conducted over a 9-month period in year 1 (July 2020 – March 2021). Aim 2 (pilot trial) will begin in the last 3 months of year 1 (April 2021) and has two parts: implementation of the pilot study with enrollment and 3 months of treatment sessions (April 2021 – December 2021) and ongoing assessment of key outcomes at 3, 6, and 12 months (through December 2022).

### **3.4 Sample Size**

A total of 75 patients will be enrolled over time, recruited over a three-month period in year 2.

We recognize that the purpose of a pilot trial with limited sample size is not to be fully powered to detect statistically significant differences on patient outcomes but rather to provide reasonably precise estimates of parameters such as acceptability and fidelity, as well as preliminary evidence of the likely magnitude of effect of the intervention on the outcomes planned for the later trial. Assuming 80% retention (consistent with our team's previous work in this population), our starting sample size of 50 intervention participants is sufficient to estimate parameters such as the proportion of participants rating the intervention as acceptable with a 95% confidence interval of  $\pm 10$ -15 percentage points, and parameters such as the proportion of FB sessions with acceptable fidelity with a 95% CI of  $\pm 6$ -8 percentage points. Our starting sample size of 25 participants in each arm, with 80% retention, is sufficient to estimate risk ratios of the effect of the intervention on outcomes that have 95% CIs that are two- to three-fold wide (e.g., RR=0.63; 95%CI = 0.38-1.00 for the presence of elevated symptoms), depending on various assumptions about outcome frequency. For comparison of effect sizes, we note that the 24-clinic cluster-randomized trial of the FB found effect sizes much stronger than this (adjusted risk ratios of 0.21 [0.15-0.29] for presence of any symptoms and 0.28 [0.22-0.34] for presence of depressive symptoms). Thus the sample size is adequate to achieve our aims.

IRB# 20-1689

Protocol v3.0 2023-10-01

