**Primary Outcomes:** *Feasibility* will be defined as the ability to successfully enroll and retain PLWH and OUD with CMDs in the pilot intervention. Feasibility will be evaluated by measuring the recruitment rate (number of patients approached to accrue the final sample). Additional indicators of feasibility will include study retention, defined as the ability to retain PLWH and OUD with CMDs in the pilot trial. Study retention will be evaluated by measuring the number of participants retained in the study (number of patients enrolled at baseline who are still enrolled in the trial), through study completion. An additional measure of intervention feasibility will be defined as the number of FB sessions attended by participants out of total FB sessions offered during the target intervention duration of 6 weeks.

*Acceptability* will be defined as the ability to deliver a culturally and resource-appropriate intervention. Acceptability will be assessed through brief exit interviews with all patient participants (n=75), HIV providers treating patients in the FB protocol, professional counselors (n=3), lay counselors (n=3), and supervising Master Trainers (n=1 per clinic, n=2 or 3 total). Exit interviews with patients will occur after the final FB session, while exit interviews with other groups will occur after the end of FB activities at each site. Exit interviews will include both closed and open-ended questions and will assess how easy the intervention was to participate in or deliver, the perceived usefulness of the intervention, and suggestions for improvement. The primary measure of acceptability will be overall participant satisfaction defined by the number of patients who were either very satisfied or somewhat satisfied with the FB among all participants who received the FB. Satisfaction will be measured on a 4-point Likert scale-- 1 indicates high satisfaction and 4 indicates high dissatisfaction.

*Fidelity* will be defined as adherence to the intervention protocol. Fidelity to session content for individual counseling sessions will be assessed by a Master Trainer by using a checklist of counseling session elements either during direct monitoring or using audio recording of up to 3 randomly chosen sessions per counselor. As we have defined in prior work, meeting or exceeding expectations at least 75% of checklist items during each

session will be considered fidelity to the intervention protocol.

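### Section 3.4 gives ±6–8 percentage points for session fidelity, but the only rating plan with a count covers about 18 sessions, or about ±14–20 points at an assumed fidelity of 90–75%

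*Combined protocol and SAP*

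**What the plan says.** Section 3.4 (Sample Size) describes the pilot's purpose as giving "reasonably precise estimates of parameters such as acceptability and fidelity". Starting from "our starting sample size of 50 intervention participants" and 80% retention, it states two precisions: ±10–15 points for the proportion of participants who find the intervention acceptable, and, for "parameters such as the proportion of FB sessions with acceptable fidelity with a 95% CI of", ±6–8 points. The section ends: "Thus the sample size is adequate to achieve our aims".

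How fidelity is measured is set out in Section 3.0, Aim 2, under Primary Outcomes. A Master Trainer completes a checklist "either during direct monitoring or using audio recording of up to 3 randomly chosen sessions per counselor". A session counts as faithful if at least 75% of its checklist items are met. The acceptability paragraph just before it lists who will give exit interviews, including "professional counselors (n=3), lay counselors (n=3"). Section 3.5 names rated audio recordings as a data source but gives no number. Nowhere does the protocol say that all or most delivered sessions will be rated.

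**The concern.** A proportion of sessions can be estimated only from sessions that someone rates. Section 3.4 bases its precision on the number of intervention participants, whereas the rating plan depends on the number of counselors, and that produces a far smaller denominator. The stated half-width looks too narrow by a factor of about two.

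Fidelity is one of three primary outcomes, and the pilot is meant to inform a fully powered trial. Someone planning that trial from Section 3.4 would expect a much sharper fidelity estimate than the counted rating plan can give. The adequacy conclusion in Section 3.4 rests partly on this figure.

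**Working it through.** **Inputs from the protocol**
- Intervention participants: 50; retention 80%, so 50 × 0.8 = 40 (Section 3.4).
- Sessions per participant: 6 (Section 3.0, FB arms), so 40 × 6 = 240 expected to be delivered.
- Sessions rated: at most 3 per counselor; counselors 3 + 3 = 6 (Section 3.0, Primary Outcomes), so 6 × 3 = 18.

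**Assumptions.** The protocol gives no expected proportion of faithful sessions; I use 75–90%. The 75% in the protocol is a per-session checklist threshold, not an expected proportion. Sessions are treated as independent unless stated.

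**Formula.** Wald 95% half-width = 1.96 × √(p(1−p)/n).

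**Reproducing the plan's figures**
- Acceptability, n = 40: 15.5 points at p = 0.5 and 9.3 at p = 0.9. The stated ±10–15 reproduces.
- Fidelity, if all 240 delivered sessions were rated: 6.3 points at p = 0.5, 5.1 at 0.8 and 3.8 at 0.9. This does not by itself reach the ±8 end.

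**Half-widths for the rating plan as counted (points)**

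| Rated sessions | p = 0.75 | p = 0.80 | p = 0.90 |
|---|---|---|---|
| 18 | 20.0 | 18.5 | 13.9 |
| 24 | 17.3 | 16.0 | 12.0 |

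For example, 1.96 × √(0.75 × 0.25/18) = 0.200. The 24-session row supposes one counselor of each type at each of the 4 clinics, which the protocol does not say. It is a sensitivity check on the counselor count.

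**Exact (Clopper–Pearson) 95% intervals**
- All counselors: 14/18, 52.4–93.6%; 16/18, 65.3–98.6%; 17/18, 72.7–99.9%; 18/18, 81.5–100%.
- One counselor type, 9 sessions: 7/9, 40.0–97.2%; 8/9, 51.8–99.7%.

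**Can any result from 18 sessions reach ±8?**
- At 17/18 no method does: exact 13.6, Wilson 12.4, Jeffreys 11.3, Wald 10.6.
- At 18/18 the half-width is 9.3 exact and 8.8 Wilson. Jeffreys gives 6.4 (87.1–100%), and Wald collapses to zero width.
- So only a unanimous result, with the Jeffreys interval, falls in the stated range. The chance of 18/18 is p^18: 0.6% at p = 0.75, 1.8% at 0.80 and 15% at 0.90.

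**Sessions needed for ±8 and ±6:** 113 and 201 at p = 0.75; 97 and 171 at 0.80; 55 and 97 at 0.90.

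**Clustering by counselor.** With 3 sessions each, the design effect is 1 + 2 × ICC. An assumed ICC of 0.05–0.20 widens the 18-session half-width to 14.5–16.4 points at p = 0.90 and 21.0–23.7 at p = 0.75.

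**The case against.** The strongest objection is that 18 is a reading, not a documented total. The limit of three may attach to audio recordings alone, leaving direct monitoring uncapped. The protocol would then give no count to contradict ±6–8. This stands as a caveat, but it does not rescue the figure: on that reading the denominator is unstated and the precision has no documented basis. Either way Section 3.4 needs correcting.

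Second, ±6–8 is an unremarkable result for a count of delivered sessions. With 240 sessions and a design effect of 1.0–1.6 (a within-participant ICC of 0–0.12, since 1 + 5 × 0.12 = 1.6), the half-width at p = 0.5 runs from 6.3 to 8.0. That may be how the figure arose, although nothing in the protocol establishes it. If so, the fault is a wrong denominator rather than a slip in calculation. It still does not describe the planned estimate, because no section says those sessions will be rated.

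Third, the counselor count comes from an exit-interview list, not a staffing plan. That is fair, but it is the only count given, and at 24 sessions the half-width is still ±12 to ±17.

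Fourth, exact intervals that treat sessions as independent ignore the clustering by counselor that Section 4.0 itself acknowledges. This is also fair. Positive within-counselor correlation would widen them, so the figures here are, if anything, kind to the protocol, and the replacement text should say so.

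**Conclusion.** The stated precision is wrong as written. If the three-session limit covers both modes of rating, the plan supports about ±14 to ±20 points rather than ±6–8, roughly twice as wide. That range rests on 6 counselors, an assumed fidelity of 90–75% and independent sessions. If the limit covers audio only, the precision cannot be derived from the protocol at all.

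This is a minor point. Section 4.0 evaluates fidelity descriptively, and no decision rule uses the half-width. It is a stated precision to correct, not a design failure.

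**What to change.** In Section 3.4, replace ±6–8 with the precision of the planned number of rated sessions, given as exact intervals for example counts. Suggested wording:

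> With up to 18 rated sessions (3 for each of 6 counselors), treated as independent, and assumed fidelity of about 75–90%, exact 95% CIs would be 52–94% if 14 of 18 sessions pass, 65–99% if 16 pass and 81–100% if all 18 pass. Within one counselor type (9 sessions) they would be 40–97% for 7 of 9 and 52–100% for 8 of 9. Correlation of sessions within counselor would widen these intervals.

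Limit the adequacy conclusion for fidelity to match.

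If the limit of three was meant for audio only, state the total number of sessions to be rated, direct and audio together, in the fidelity paragraph of Section 3.0, and compute the precision from that total.

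Rating may already be finished: Section 3.3 plans "ongoing assessment of key outcomes at 3, 6, and 12 months (through December 2022"), and this version is dated 1 October 2023. In that case, report the number of sessions actually rated with its exact interval.

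The cost is wording in Section 3.4 and perhaps one clarifying phrase in Section 3.0, together with a less favourable stated precision. No extra patients, visits or ratings are needed.
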